##### *4.8.3.2.3 Modulations of circulating CEA as a potential PD biomarker of response to tusamitamab ravtansine treatment*

A graphical visualization (spaghetti plot) will be presented to visualize the relative change from baseline of circulating CEA values for each participant, annotated with the best overall response.

#### **4.9 INTERIM ANALYSES**

No formal interim analysis is planned in this study.

The study analysis will be conducted in 2 steps.

The first analysis step will be conducted when all evaluable treated participants have had at least 2 post-baseline tumor assessments, experienced confirmed objective response, or have discontinued the study for any reason. This study cut-off will occur approximately 6 months after the date of the first IMP administration of the last participant: 4 months for 2 tumor assessments and 2 months if a confirmation of response is needed.

The final analysis will be conducted at the end of the study. All analyses will be updated at this time.

For each analysis step, the analysis cut-off date will be defined as the date of the database extraction that will be performed for the analysis after the cut-off (study cut-off for the first analysis step).

Analyses methods and conventions described in the other sections of this SAP will be applied for all analyses as applicable. The following additional rules will apply at the first analysis step:

- Participants without end of treatment status performed at the time of the analysis cut-off date will be considered as ongoing. Therefore:
  - Participants who did not discontinued the study intervention at analysis cut-off date will be analyzed as “ongoing” in the disposition summary.
  - Their treatment-emergent (TE) period and concomitant medication period will end at the analysis cut-off date.

## 5 SUPPORTING DOCUMENTATION

### 5.1 APPENDIX 1 LIST OF ABBREVIATIONS

ADC:	antibody drug conjugate
ADI:	actual dose intensity
AE:	adverse event
AESI:	adverse event of special interest
ALP:	alkaline phosphatase
ALT:	alanine aminotransferase
aPTT:	activated partial thromboplastin time
AST:	aspartate aminotransferase
ATA:	antitherapeutic antibody
AUC:	area under the curve
BCVA:	best corrected visual acuity
BOR:	best overall response
BSA:	body surface area
BUN:	blood urea nitrogen
CEA:	carcinoembryonic agent
CEACAM5:	carcinoembryonic antigen-related cell adhesion molecule 5
CI:	confidence interval
COVID-19:	coronavirus disease 2019
CR:	complete response
CV:	coefficient of variation
DLT:	dose-limiting toxicity
DOE:	duration of response
ECG:	electrocardiogram
ECOG:	Eastern Cooperative Oncology Group
e-CRF:	electronic case report form
EOT:	end of treatment
HLGT:	high-level group term
HLT:	high-level term
ICI:	immune checkpoint inhibitor
IHC:	immunohistochemistry, immunochemistry
IMP:	investigational medicinal product
INR:	international normalized ratio
LDH:	lactate dehydrogenase
LLN:	lower limit of normal
LLOQ:	lower limit of quantitation
LLT:	lower-level term
MedDRA:	Medical Dictionary for Regulatory Activities
NCI-CTCAE:	National Cancer Institute Common Terminology Criteria for Adverse Events
NSQ NSCLC:	non-squamous non-small cell lung cancer
ORR:	objective response rate

PCSA:	potentially clinically significant abnormalities
PD:	progressive disease
PDI:	planned dose intensity
PD-L1:	programmed death-ligand 1
PFS:	progression-free survival
PK:	pharmacokinetic
PR:	partial response
PS:	performance status
PT:	preferred term
Q1:	quartile 1
Q3:	quartile 3
RBC:	red blood cells
RD1:	relative dose intensity
RECIST:	response evaluation criteria in solid tumors
RP2D:	recommended Phase 2 dose
SAE:	serious adverse event
SAP:	statistical analysis plan
SD:	standard deviation
SE:	standard error
SMQ:	standardized MedDRA queries
SOC:	system organ class
TEAE:	treatment-emergent adverse event
TKI:	tyrosine kinase inhibitor
ULN:	upper limit of normal
ULOQ:	upper limit of quantitation
WBC:	white blood cells
WHO-DD:	World Health Organization-drug dictionary

## 5.2 APPENDIX 2 DEMOGRAPHICS AND BASELINE CHARACTERISTICS, PRIOR OR CONCOMITANT MEDICATIONS

### *Demographics, baseline characteristics, medical surgical history*

The following demographics and baseline characteristics, medical and surgical history and disease characteristics at baseline will be summarized using descriptive statistics in the all-treated population.

#### Demographic and baseline characteristics

- Age in years as quantitative variable and in categories (<65, [65-75[,  $\geq 75$ )
- Sex (Male, Female)
- Race (American Indian or Alaska Native, Asian, Black or African American, Native Hawaiian or Other Pacific Islander, White, Not reported, Unknown)
- Ethnicity (Hispanic or Latino, not Hispanic or Latino, Not reported, Unknown)

- ECOG PS (0, 1)
- Weight in kg as quantitative variable
- BSA in m^2 as quantitative variable

Baseline safety and efficacy parameters (apart from those listed above) will be presented along with the safety and efficacy summaries.

Medical (or surgical) history includes relevant history of previous pathologies and surgeries. Medical and surgical history will be coded to a LLT, PT, HLT, HLGT, and associated primary SOC using the MedDRA version currently in effect at Sanofi at the time of database lock.

Specific disease history includes primary tumor site, histopathology type, staging, time from initial diagnosis to first administration of IMP (in years).

Specific disease status at study entry includes extent of diseases, number and type of organs involved (both including and excluding primary tumor location), PD-L1 expression (<1%, ≥1%), smoking status (current, former, never) and smoking habits (in pack-years).

CEACAM5 expression, circulating CEA (<100 µg/L, ≥100 µg/L, <80 µg/L, ≥80 µg/L, <50 µg/L, ≥50 µg/L, <5 µg/L, ≥5 µg/L and <3 µg/L, ≥3 µg/L) and type of tumor biopsy (archival /fresh) will also be described.

### ***Prior or concomitant medications***

All medications will be coded using the World Health Organization-Drug Dictionary (WHO-DD) using the version currently in effect at Sanofi at the time of database lock.

- Prior medications are those the participant received prior to first IMP intake. Prior medications can be discontinued before first administration or can be ongoing during treatment period.
- Concomitant medications are any medications received by the participant concomitantly to any IMP from the first administration of IMP to the last IMP intake + 30 days.
- Post-treatment medications are those the participant received in the period running from the end of the concomitant medications period up to the end of the study.
- A given medication can be classified as a prior medication and/or as a concomitant medication and/or as post-treatment medication. If it cannot be determined whether a given medication was received prior or concomitantly or post, it will be considered as prior, concomitant, and post-treatment medication.

The prior and concomitant medications will be summarized for the all-treated population, by anatomic and therapeutic level. Participants will be counted once in each ATC category (anatomic or therapeutic) linked to the medication.

### ***Premedications***

As defined in Section 6.1 of the study protocol, participants receive premedications prior to ramucirumab administration to prevent from infusion related allergic reactions to tusamitamab ravtansine and/or ramucirumab. Premedications are defined as non-investigational medicinal products and are reported on a specific e-CRF page.

Number (%) of participants treated with dexamethasone and number (%) of participants treated with Histamine H1 antagonist after 4 cycles will be provided. In addition, number of cycles of participants treated with Histamine H1 antagonist will be summarized as a quantitative variable.

### ***Anticancer therapies***

Prior anticancer therapies include anticancer treatment, surgery related to lung cancer and radiotherapy.

- Number (%) of prior anticancer therapies including neoadjuvant, adjuvant and advanced regimen
- Number (%) of participants with intent:
  - Neoadjuvant and adjuvant and advanced
  - Neoadjuvant or adjuvant and advanced
  - Neoadjuvant or adjuvant only
  - Advanced only
- Number (%) of prior anticancer therapies in the advanced setting
  - A regimen in the advanced setting consists of a single agent, combination, or a sequential therapeutic strategy with several drugs, given until a PD is documented.
  - Adjuvant/neoadjuvant treatment for a participant who relapsed with metastatic disease during or within 6 months of treatment will be considered as first line treatment in the advanced setting.
- Type of prior anticancer treatment including neoadjuvant, adjuvant and advanced regimens:
  - Biologics and small molecules
    - Tyrosine kinase inhibitor (TKI): EGFR inhibitors, anti-angiogenic, BRAF kinase inhibitors, ALK inhibitors, RAS/RAF/MEK/ERK signaling pathway inhibitors, ROS1 inhibitors
    - Immune checkpoint inhibitor (ICI): anti-PD1/PD-L1, CTL4A inhibitors
    - Others
  - Chemotherapy: platinum, pemetrexed, antimicrotubules, gemcitabine, others
  - Antibody drug conjugate (ADC)
  - Others
- Prior immune checkpoint inhibitor: Sequential or Combination with chemotherapy

- Summary of last prior anticancer therapy:
  - Time from completion of last regimen to first administration of IMP (in months)
  - Main treatments of last regimen:
    - ICI monotherapy
    - ICI in combination with chemotherapy
    - ICI and other biologics and small molecules
    - No ICI: Chemotherapy, Biologics, or Chemotherapy and Biologics
  - Best response to the last regimen
  - Reason for discontinuation of the last line
- Prior surgery: number (%) of participants with any prior surgery related to cancer, type of surgery and time from the last surgery to the first administration of IMP (in years)
- Prior radiotherapy: number (%) of participants with any prior radiotherapy related to cancer, intent, analgesic intent if palliative and time from last dose of radiotherapy to first administration of IMP (in years)

Further anticancer therapies (including systemic anticancer therapies, surgeries and radiotherapies) after discontinuation of study intervention will be summarized based on WHO-DD coding.

### 5.3 APPENDIX 3 DATA HANDLING CONVENTIONS

#### Unscheduled visits

Unscheduled visit measurements will be used for computation of baseline and worst treatment-emergent values and/or grades.

Unscheduled tumor assessments will be used for computation of efficacy endpoints based on radiological assessments of tumor burden.

### 5.4 APPENDIX 4 SANOFI SPONSOR GENERIC RANGES FOR HEMATOLOGICAL AND BIOCHEMISTRY PARAMETERS

The current list of generic ranges (for adults) for hematological, coagulation and biochemistry parameters (3) are provided in tables below.

**Table 12 - Generic ranges for hematological and coagulation parameters**

Parameter	Gender	Unit	LLN	ULN
Basophils		10  /L	0	0.15
Eosinophils		10  /L	0	0.4
Erythrocytes (RBC) count	M	10  /L	4.5	5.9
Erythrocytes (RBC) count	F	10  /L	4	5.2

Parameter	Gender	Unit	LLN	ULN
Hematocrit	M	Fraction of 1	0.41	0.53
Hematocrit	F	Fraction of 1	0.36	0.46
Hemoglobin	M	g/L	135	175
Hemoglobin	F	g/L	120	160
Leukocytes (WBC) count		10  /L	4.5	11
Lymphocytes		10  /L	1	2
Monocytes		10  /L	0.18	0.5
Neutrophils		10  /L	1.8	3.15
Platelets count		10  /L	150	350
Prothrombin time		INR	0.8	1.2

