9.4.2.4 Analysis of clinical laboratory evaluations

Clinical laboratory values will be analyzed after conversion into standard international units. International units will be used in all listings and tables.

Hematology and clinical chemistry results will be graded according to the NCI-CTCAE V5.0, when applicable. Number and percentage of participants with laboratory abnormalities (all grades and by grade) using the worst grade during the treatment period will be provided for the all-treated population.

When the NCI-CTCAE V5.0 grading scale is not applicable, the number of participants with laboratory abnormality out-of-normal laboratory range value will be displayed.

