#### 4.7.3 Additional safety assessments

##### 4.7.3.1 Laboratory variables, vital signs and electrocardiograms (ECGs)

The following laboratory variables, vital signs and electrocardiogram (ECG) variables will be analyzed. They will be converted into standard international units.

- Hematology and coagulation:
  - Red blood cells and platelets and coagulation: hemoglobin, hematocrit, red blood cell (RBC) count, platelet count, prothrombin time (expressed as international normalized ratio [INR]) and activated partial thromboplastin time (aPTT),
  - White blood cells: white blood cell (WBC) count, neutrophils, lymphocytes, monocytes, basophils and eosinophils.
- Clinical chemistry:
  - Metabolism: glucose, total protein, and albumin,
  - Electrolytes: sodium, potassium, and corrected calcium. Corrected calcium (mmol/L) will be derived using the following formula: measured total calcium (mmol/L) +  $0.8 \times 0.25 \times (4.0 - [\text{serum albumin } \{g/L\} \times 0.1])$ , where 4.0 represents the average albumin level,
  - Renal function: creatinine, blood urea nitrogen (BUN) and urea,
  - Liver function: alanine aminotransferase (ALT), aspartate aminotransferase (AST), alkaline phosphatase (ALP), lactate dehydrogenase (LDH), total and direct bilirubin,
  - Circulating carcinoembryonic antigen (CEA).

- Urinalysis:
  - Urine dipstick: proteins,
  - Urinalysis: proteins assessed on 24 hour urine collection.
- Vital signs: heart rate, systolic and diastolic blood pressure, weight and ECOG Performance Status (PS).
- ECG variables: PR, QRS, QT and corrected QTcF (according to Fridericia).
- $QTcF=QT/RR^{0.33}$ .

where RR interval (in seconds) = 60/HR, and HR = heart rate in beats per minute (from the ECG form).

Data below the lower limit of quantitation/detection limit (LLOQ) will be replaced by half of the LLOQ, data above the upper limit of quantification will be replaced by ULOQ value.

For hematological parameters and some selected coagulation and biochemistry parameters, Sanofi sponsor generic ranges (LLN, ULN) are defined and will be used for grading (see list of parameters in [Section 5.4](#)). For other coagulation and biochemistry parameters, grading will be derived using local laboratory normal ranges.

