### **Analyses according to potentially clinically significant abnormalities (PCSA) and NCI grading**

For laboratory variables, analyses according to NCI grading will be made based on NCI-CTCAE Version 5.0. In addition, for laboratory variables for which the NCI-CTCAE scale is not applicable, such as vital signs and ECG variables, PCSA analyses will be performed based on the PCSA list currently in effect at Sanofi at the time of the database lock.

Analyses according to PCSA and NCI grading will be performed based on the worst value during the treatment-emergent period, using all measurements (either local or central, either scheduled, nonscheduled or repeated).

QTcF prolongation will be graded according to NCI-CTCAE version 5.0. The frequency of participants each grade of QTcF prolongation during the on-treatment period will be summarized. For participants with multiple occurrences of QTcF prolongation during the treatment, the maximum grade per participant will be used.

For laboratory variables, vital signs and ECG variables above, the incidence of participants with at least one PCSA during the treatment-emergent period will be summarized regardless of the baseline level and according to the following baseline status categories:

- Normal/missing
- Abnormal according to PCSA criterion or criteria

The number (%) of participants with QTcF abnormality worsening during the on-treatment period (worst value per participant) will be displayed.

For laboratory variables graded by NCI-CTCAE,

- The number (%) of participants with abnormal laboratory tests at baseline will be presented by grade.
- The number (%) of participants with an abnormal laboratory test during the treatment-emergent period will be summarized by grade. When appropriate, the number (%) of participants with abnormality of any grade and with Grade 3-4 abnormalities will be provided.
- For liver function test abnormalities, the baseline status will be provided according to multiples of the upper limit of normal (ULN) for each test.

For laboratory variables graded neither by NCI-CTCAE nor by PCSA, the number (%) of participants with laboratory test results outside normal ranges will be provided.

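### SAP Table 12: the five differential upper limits sum to 6.2, which is incompatible with the WBC upper limit of 11 in the same table

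*SAP*

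**What the plan says.** SAP Appendix 4 (Section 5.4), Table 12, gives generic adult ranges in ×10⁹/L, attributed to SAP reference 3. The row "Leukocytes (WBC) count" has limits 4.5 and 11. The differential rows include "Lymphocytes 10 9 /L 1 2", "Monocytes 10 9 /L 0.18 0.5", "Eosinophils 10 9 /L 0 0.4" and "Basophils 10 9 /L 0 0.15" (lower limit, then upper limit). Neutrophils are given as 1.8 to 3.15.

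SAP 4.7.3.1 makes the table operative. For hematology parameters, "Sanofi sponsor generic ranges (LLN, ULN) are defined and will be used for grading", while coagulation and biochemistry parameters outside the tables keep local laboratory ranges. The same section lists exactly these five cell types under white blood cells.

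Reporting follows an order. Laboratory variables are graded by NCI-CTCAE v5.0, or assessed against the sponsor's PCSA list where CTCAE does not apply. Where neither applies, "the number (%) of participants with laboratory test results outside normal ranges will be provided". Protocol 9.4.2.4 has no PCSA step: where CTCAE grading does not apply, "the number of participants with laboratory abnormality out-of-normal laboratory range value will be displayed". It does not say whether that range is the sponsor's generic one.

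**The concern.** The five types in the differential are the components of the white count. One would expect their upper limits to sum to at least the WBC upper limit; otherwise a patient with a high-normal WBC cannot have a normal differential. Here the sum falls well short.

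Laboratory abnormalities according to CTCAE are a secondary endpoint for the doublet cohort, and the out-of-range displays sit beside them. If a ULN is too low, ordinary counts are recorded as high. The study has a single arm, so there is no control group in which the same artefact would show.

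**Working it through.** **Inputs** (SAP Table 12, ×10⁹/L)

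| Parameter | LLN | ULN |
|---|---|---|
| Neutrophils | 1.8 | 3.15 |
| Lymphocytes | 1 | 2 |
| Monocytes | 0.18 | 0.5 |
| Eosinophils | 0 | 0.4 |
| Basophils | 0 | 0.15 |
| WBC | 4.5 | 11 |

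The SAP states no total for the differential limits, so there is no figure of its own to reproduce.

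**Sum of the ULNs.** 3.15 + 2 + 0.5 + 0.4 + 0.15 = 6.20, which is 11 − 6.20 = 4.80 below the WBC ULN.

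**Consequence.** Suppose the five types make up essentially the whole WBC. If every type is at or below its ULN, WBC is at most 6.20. So a WBC above 6.20 forces at least one type above its ULN.

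**Share of the normal range.** (11 − 6.2)/(11 − 4.5) = 4.8/6.5 = 73.8%. The midpoint, (4.5 + 11)/2 = 7.75, lies inside this part.

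**Size of the excess.** Put the other four types at their ULNs: 2 + 0.5 + 0.4 + 0.15 = 3.05. Neutrophils must then be 7.75 − 3.05 = 4.70 at mid-range, and 11 − 3.05 = 7.95 at the top, against a ULN of 3.15.

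**Lower limits.** 1.8 + 1 + 0.18 + 0 + 0 = 2.98, below the WBC LLN of 4.5. There is no conflict on the low side.

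**From range width to share of normal counts.** This needs a WBC distribution, which the documents do not give. As an assumption, take 4.5 to 11 as the central 95% and compute P(6.2 < WBC ≤ 11)/P(4.5 ≤ WBC ≤ 11):

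- Normal, mean 7.75, SD 3.25/1.96 = 1.66: about 84%.
- Log-normal, log-SD (ln 11 − ln 4.5)/(2 × 1.96) = 0.228: about 72%.
- Same log-SD with the median moved: about 37% at 5.5, 49% at 6.0, 54% at 6.2 and 71% at 7.0.

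**The case against.** The strongest reply is that exceeding a ULN is not in itself a reported abnormality. Under SAP 4.7.3.1, a bare out-of-range result is counted only for variables covered by neither CTCAE nor PCSA. The sum argument forces only one of the five types over its limit, and that type can be neutrophils. The one neutrophil scale printed in the documents (protocol Appendix 4) grades decreases and has no high side. A WBC between 6.2 and 11 therefore need not produce any reported abnormality. This stands: a reader might infer that such counts must be flagged, but that depends on CTCAE v5.0 and the PCSA list, neither of which is reproduced.

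A reader might also infer that most normal white counts are affected. The 74% is a share of range width, not of counts. Under the log-normal assumption, the share of normal counts is just under half at a median of 6.0 and lower below that.

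A third tempting step is to reconstruct the correct limits. The neutrophil limits are exactly 40% and 70% of the WBC lower limit (1.8/4.5 and 3.15/4.5), and the monocyte LLN is 4% of it (0.18/4.5). This suggests percentages applied to the wrong end of the WBC range. The SAP does not state how the limits were derived, so rescaling them to 11 would be guesswork.

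The impact is also limited: safety analyses are descriptive with no testing, and the endpoint is framed by CTCAE. None of this removes the contradiction in the table or the fact that the SAP names these ranges as a grading input.

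**Conclusion.** The inconsistency holds, and it is exact: 6.2 against 11. It rests on one assumption, that the five listed types make up essentially all white cells. Given that, 74% of the width of the table's normal WBC range cannot have an all-normal differential, and the two sets of upper limits cannot both be right.

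Any high-side grade or out-of-range count that uses these ULNs would be inflated, at baseline and on treatment. How many participants this touches cannot be determined from the documents.

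Grading of decreases is unaffected, because the upper limits play no part in it. DLT incidence and ORR do not use these ULNs either. The point concerns the accuracy of descriptive safety tables and does not bear on the primary results.

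**What to change.** Before database lock, check the five differential ULNs in Table 12 against SAP reference 3 and correct them so that they are compatible with the WBC ULN of 11. Alternatively, use local laboratory normal ranges for the differential, as SAP 4.7.3.1 already does for coagulation and biochemistry parameters without a generic range. Do not adopt back-calculated limits without checking them against the source.

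It would also help to state in SAP 4.7.3.1 which differential variables have a high-side CTCAE or PCSA criterion and which fall to the out-of-range count, so that a reader can see where the ULNs matter.

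The cost is one SAP table and the matching programming lookup, with a rerun of any laboratory outputs already produced from it. If local ranges are chosen instead, the sentence in 4.7.3.1 changes too. No study procedure or data collection changes.

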**Table 13 - Generic ranges for biochemistry parameters**

Parameter	Unit	LLN	ULN
Albumin	g/L	35	55
Blood Urea Nitrogen (BUN)	mmol/L	3.6	7.1
Corrected calcium	mmol/L	2.2	2.6
Glucose	mmol/L	3.9	7
Potassium	mmol/L	3.5	5
Sodium	mmol/L	136	145
Protein	g/L	55	80
Urea	mmol/L	3.6	7.1

